The analysis is stratified by two important factors, risk of recurrence (low, intermediate, high) and type of initial treatment (surgery, radiation); thus, 6 separate analyses will be performed. All outcomes will be defined from years 2-10 from end of prostatectomy or radiation treatment (Figure 1). We will use two modeling strategies to evaluate our outcomes of interest: 1) modified Poisson/binary regression^{19,20} with sandwich standard errors to estimate risks of the events of interest during a set follow-up period; and 2) Cox Proportional Hazards regression [CI-3]. Using the modified Poisson/binary regression models, we will estimate the risk of experiencing the outcome of interest (death, recurrence, use of procedures and tests, treatment for recurrence) during a defined interval beginning in the second year following treatment. Additionally, we will estimate overall survival using adjusted Cox Proportional Hazards regression models. We will evaluate the proportional hazards assumption by generating Kaplan-Meier survival curves and through testing interactions between relevant covariates and time in the Cox model. Covariates that violate the proportional hazards assumption will be used as stratification variables as appropriate. In sensitivity analyses, we will generate a propensity score (where the patient, provider and hospital characteristics measured at the time of prostatectomy or radiation completion are included in the propensity score) and create a matched cohort of patients to evaluate using Kaplan-Meier survival models [described in detail in C3]. For secondary outcomes, time to recurrence will be modeled for each surveillance frequency using a competing risk analysis as described by Fine and Gray.²¹ Similar methods will be used to calculate the cumulative incidence of procedures and tests and treatment for recurrence.

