Several outside/environmental factors can affect a patient's surveillance frequency. In our preliminary analysis using the US population-based Surveillance, Epidemiology and End Results (SEER)-Medicare dataset, we found race, marital status, and regional socioeconomic determinants (high school graduation rate) to be associated with different PSA surveillance frequencies. The NCDB captures a comprehensive list of covariates (see above). We will examine if surveillance frequency is associated with each individual factor and account for these factors using modeling as above. Finally, we recognize that there may still be important unmeasured confounders in our study; therefore, we plan to use sensitivity analyses to estimate the impact of a hypothetical unmeasured/unobserved confounder, using similar methodology used in a prior study by the co-I ([name]).²² This analysis will allow us to determine the extent of confounding that would substantively change our study findings.

A conceptual diagram (directed acyclic graph) demonstrating the relationship between measured covariates and our selected study outcomes for Aim 1 is provided in Figure 2 below.

Figure 2. Directed Acyclic Graph for the Hypothesized Relationship between Selected Study Variables and Outcomes for Aim 1

Footnote: Analyses will be stratified by the type of initial treatment (surgery, radiation) and recurrence risk (low, intermediate, high) and the hypothesized relationships may vary somewhat by each clinical scenario. Relationship between variables identified as pertaining to Aim 2 are noted in Figure 3.

Statistical power: There are >1,400 CoC-accredited hospitals. With 10 patients sampled at each hospital, we expect 14,000 patients will be available for analysis. We will intentionally sample approximately the same number of patients in each of the 6 cohorts (risk group x primary treatment), providing 2,333 patients in each cohort. Within each cohort, patients receiving different surveillance frequencies will be compared. Based on preliminary analysis of SEER-Medicare data, the national patterns of PSA surveillance in the first year are: (Table 2)

Number of PSAs	Low Risk	Intermediate Risk	High Risk
1	20%	18%	17%
2-3	61%	59%	53%
4	19%	23%	30%

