From Medical records: age at diagnosis, comorbidities (scored using the validated Charlson index), prostate cancer diagnosis (low, intermediate, high risk), treatments;

From patient report: education, household income, race/ethnicity, insurance, marital status, employment.

Data Analysis [IR-3]: Consistent with prostate cancer HRQOL literature, we will treat each patient-reported outcome measure as a continuous variable. We will model changes in anxiety (primary outcome) and HRQOL (secondary outcomes) from the first time point through 60 months using repeated measures methodology such as generalized estimating equations to examine change over time while controlling for patient related covariates. Models will be estimated using PROC GENMOD (SAS 9.4) with an identity link and normal distribution for continuous variables. Models will account for the covariates described above. For the primary outcome of anxiety, we will compare the overall anxiety score among comparison groups, as well as scores for each of the 3 subscales to determine if there is a particular aspect of anxiety which differs by surveillance frequency. For PCSI, scale scores for sexual, urinary, and bowel function will be compared across groups. For the SF-12, mental and physical component scores will be calculated and compared.

A conceptual diagram (directed acyclic graph) demonstrating the relationship between measured covariates and our selected study outcomes for Aim 2 is provided in Figure 3 below. Of note, we anticipate similar relationships between the categories of variables identified in the “other key covariates” section of the directed acyclic graph below to mirror those in Aim 1 / Figure 2. For ease of interpretation we focus primarily on the relationship between variables unique to Aim 2 in the graphic below.

Figure 3. Directed Acyclic Graph for the Hypothesized Relationship between Selected Study Variables and Outcomes for Aim 2

Footnote: Analyses will be stratified by the type of initial treatment (surgery, radiation) and recurrence risk (low, intermediate, high) and the hypothesized relationships may vary somewhat by each clinical scenario.

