Statistical power: A total of 1,079 participants have completed MAX-PC (primary outcome), PCSI and SF12 (secondary outcomes) at 12 months. If there is attrition of 25% from 12 to 60-month time points, that leaves N=809 with complete data. Using the distributions in Table 2, this sample size provides >90% power to detect a $\frac{1}{2}$ -standard deviation (clinically significant) difference in anxiety among the different surveillance frequency groups. More specifically, a sample size as small as 154 in each group will provide 90% power to detect $\frac{1}{2}$ -standard deviation difference among groups. For secondary outcomes PCSI and SF-12, assuming a standard deviation of 10,^{36,37} we have >90% power to detect clinically meaningful differences (1/2 standard deviation = 5 points) among groups. All $\alpha=.05$; two-sided tests.

Potential problems and alternative strategies: Patients with different baseline HRQOL and anxiety may receive different surveillance frequencies. The longitudinal design of Aim 2 and availability of pre-treatment data allow us to analytically account for these potential differences among comparison groups. We do not have MAX-PC data pre-treatment, but will examine if pre-treatment anxiety (an item on SF-12) differs by surveillance frequency groups. If so, we will adjust for this baseline anxiety measure in data analysis. We will address potential clustering as described on Page 6.

We will evaluate the extent to which attrition impacts our analysis and subsequent interpretation. We have planned multiple sensitivity analyses to ensure the robustness of our findings, including

evaluations of the impact of a hypothetical unmeasured confounder, instrumental variables analysis, stratification and restriction.

C3. Avoidance of bias [IR-3][GM-3][CI-5][CI-6]: The large population cohorts used in Aim 1 and Aim 2 will provide a high level of evidence from real-world settings. The following analytic methods to minimize bias and confounding are consistent with the PCORI Methods Report (“Standards for Causal Inference Methods,” dated 3/15/12) and the recent AHRQ publication, “Developing a Protocol for Observational Comparative Effectiveness Research, A User’s Guide.”

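### Aim 2 power text: the pooled >90% is right, but the 154-per-group sentence is wrong, the 5-point PCSI claim rests on the SF-12 standard deviation, and the >90% should be tied to the pooled analysis (minor)

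*Combined protocol and SAP*

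**What the plan says.** Specific Aim 2, Statistical power, starts from 1,079 men with 12-month questionnaires and assumes 25% attrition by 60 months: "that leaves N=809 with complete data". It then states "Using the distributions in Table 2, this sample size provides >90% power to detect a" half-SD difference in anxiety, and adds that as few as 154 per group give 90% power for that difference. For PCSI and SF-12 together it assumes an SD of 10, citing references 36 and 37, and equates half an SD with 5 points. All tests are two-sided at 0.05.

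Under Outcomes, the same two references support the SF-12 norm-based scoring (mean 50, SD 10). The PCSI is described there as a 0 to 100 symptom score, with no SD.

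On the analysis, the Aim 2 Data Analysis text models the outcomes "using repeated measures methodology such as generalized estimating equations to examine change over time" and says "Models will account for the covariates described above". Those covariates include "prostate cancer diagnosis (low, intermediate, high risk), treatments". The Figure 3 footnote says "Analyses will be stratified by the type of initial treatment (surgery, radiation) and recurrence risk". The same sentence stands under Figure 2 for Aim 1, where the Data Analysis text adds "thus, 6 separate analyses will be performed". Aim 2 has no such addition, and its section on potential problems lists stratification among the sensitivity analyses.

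**The concern.** The 154 sentence pairs a sample size with a power that do not belong together, so anyone checking the calculation will fail to reproduce it.

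The PCSI statement is in points, and points can be converted to SD units only with an SD for that scale. The plan borrows one that SF-12 has by construction. If PCSI scores vary more than that, 5 points is less than half an SD and the >90% may not hold for it.

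The footnote raises a question of scope. The section's only power figure is for 809 men analysed together, and no Aim 2 stratum sizes are given. If results are reported for six treatment-by-risk strata, a reader could carry the >90% over and take a null result in one stratum as excluding a half-SD difference in anxiety.

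**Working it through.** **Inputs.** N = 1,079 x 0.75 = 809 (Aim 2, Statistical power). Shares with 1, 2-3 and 4 PSA tests from Table 2, the last row read as at least 4: low risk 20/61/19%, intermediate 18/59/23%, high 17/53/30%. Two-sided 0.05, difference d = 0.5 SD.

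**Formula.** Power = Φ(d / √(1/n1 + 1/n2) − 1.960), a two-sample normal approximation.

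**1. The plan's pooled figure.** The weakest contrast is 1 versus at least 4 tests.
- Low-risk shares: 161.8 vs 153.7. √(1/161.8 + 1/153.7) = 0.1126; 0.5/0.1126 − 1.960 = 2.48; power 99.3%.
- Intermediate shares: 145.6 vs 186.1, 99.5%.
- High-risk shares: 137.5 vs 242.7, 99.7%.
- All other pairs: at least 99.9%.

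The >90% is therefore reproduced.

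**2. The 154 sentence.** √(2/154) = 0.1140; 0.5/0.1140 − 1.960 = 2.43; power 99.2%. The alternatives tried do not give 90% at 154 either:

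| Test | Power at 154 per group | n per group for 90% |
|---|---|---|
| Pairwise t-test | 99.2% | 86 (85 gives 89.99%) |
| Three-group F test, third mean midway (f = 0.204) | 98.1% | 103 |
| Bonferroni, 0.05/3 | 97.7% | 109 |

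The difference that 154 per group detects with 90% power is (1.960 + 1.282) x √(2/154) = 3.242 x 0.1140 = 0.37 SD. The number itself matches 19% x 809 = 153.7, the expected low-risk group with the most tests.

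**3. PCSI in points.** For a single unadjusted score at N = 809, the largest SD at which 5 points has 90% power on every contrast is 5/(3.242 x 0.1126) = 13.7. No PCSI SD is given, so the values below are assumptions. Ranges run over all contrasts and all three sets of Table 2 shares.

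| Assumed SD | Power for 5 points, one score, N = 809 |
|---|---|
| 15 | 84-99% |
| 20 | 60-88% |
| 25 | 43-70% |

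The limit rises with a more efficient analysis. For the mean of five annual scores at assumed within-patient correlation r = 0.5, the variance factor is (1 + 4 x 0.5)/5 = 0.6 and the limit is 13.7/√0.6 = 17.7. With baseline adjustment as well, the factor is 0.6 − 0.5² = 0.35 and the limit is about 23.

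**4. Strata, as an illustration.** Assume six equal strata, 809/6 = 135 each, with Table 2 shares and 1 versus at least 4 tests.

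| Risk group | n | One score | Mean of five scores, r = 0.5 |
|---|---|---|---|
| Low | 27 vs 26 | 44.1% | 64.8% |
| Intermediate | 24 vs 31 | 45.4% | 66.3% |
| High | 23 vs 41 | 48.1% | 69.5% |

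If imputation retained all 1,079 (180 per stratum), the two ranges become 55-60% and 77-81%.

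These figures depend on the estimand. For a 12-to-60-month change, with the 0.5 taken in SDs of the raw score, the variance factor is 2(1 − r). In strata of 135, power is then again 44-48% at r = 0.5 (factor 1), but 98-99% at r = 0.9.

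**The case against.** The strongest reply is that the quoted power sentence is true and claims nothing about strata. It speaks of 809 patients, and the model text, the covariate list and the placing of stratification among the sensitivity analyses all point to one pooled, adjusted model. The footnote belongs to a conceptual diagram and repeats the Aim 1 wording. Equal strata come from the Aim 1 sampling plan, and the Aim 2 cohort was not sampled that way. All of this stands. It reduces the stratum point to an inconsistency to be reconciled, with illustrative figures.

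A reader might infer that Aim 2 is underpowered for its primary outcome, or that six separate Aim 2 analyses are planned. The documents support neither. A reader might also infer that the strata can reach 90% only if within-patient correlation is low. That holds for a mean level over time and reverses for a change score; the Aim 2 text speaks both of modelling change and of comparing overall scores. So no general limit on the correlation can be stated.

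On the 154 sentence, it can be said that at least 90% would be true. That is so, but the wording presents 154 as the number needed for 90%, and it is not.

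On PCSI, the plan labels its SD an assumption, power for half an SD does not depend on it, and the pre-treatment PCSI scores can be used for adjustment. This also stands. What remains is that nothing in the documents makes 5 points half an SD on that instrument.

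**Conclusion.** Minor, and a matter of wording and sourcing.

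- **Pooled anxiety power** is sound: at least 99.3% for half an SD on every contrast at N = 809.
- **The 154 sentence** is wrong by calculation alone. The error is conservative and changes no conclusion.
- **The PCSI 5-point claim** is unsupported, which is not the same as false. The SD limit of 13.7 applies to one unadjusted score; repeated scores or baseline adjustment raise it.
- **The footnote and the analysis text** conflict on the place of stratification, and the >90% should not be read as covering each of six strata. The 44-48% and 65-70% figures rest on equal strata, Table 2 shares and, for the second, an assumed correlation of 0.5 with a mean-level estimand.

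**What to change.** 1. Restate the 154 sentence: 154 per group gives about 99% power for half an SD, or 90% for 0.37 SD; about 86 per group gives 90% for half an SD.
2. Recompute PCSI power for each scale from the SDs in the cohort's existing baseline and 12-month data, or state it in SD units only. The 5-point figure can stay for SF-12.
3. Reconcile the Figure 3 footnote with the Data Analysis text by naming the pooled, covariate-adjusted model as the primary Aim 2 analysis. Tie the >90% to that model, and report six-stratum results as exploratory without that claim.
4. If six separate analyses are in fact intended, give the stratum sizes and the power of each, with the estimand and the within-patient correlation used.

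The cost is wording and one recalculation from data already collected, with no extra patients or follow-up. The PCSI statement may become less favourable, and the stratum results lose any claim to the >90%.

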Primary outcome: Our stakeholders identified anxiety and HRQOL (see below) as potential harms of frequent surveillance. The *validated* Memorial Anxiety Scale for Prostate Cancer (MAX-PC)²⁴ will be used as primary outcome for Aim 2. This instrument contains 18 questions assessing anxiety related to prostate cancer (11 items, total score 0 to 33), PSA testing (3 items, total score 0 to 9), and fear of recurrence (4 items, total score 0 to 12). A higher score in each subscale indicates more anxiety.

Secondary outcomes: Prostate cancer treatments can have detrimental HRQOL effects, including effects on urinary, bowel and sexual function symptoms,²⁵ and global quality of life.²⁶ However, HRQOL outcomes in patients who receive different post-treatment surveillance frequencies have not been previously studied. It is likely (we hypothesize) that more frequent surveillance will detect more recurrences, leading to more procedures and treatments resulting in worse HRQOL.

If indeed more frequent surveillance is associated with worse HRQOL, this is critically important data to inform patients about the trade-offs (potential benefit: improved survival; harm: worse HRQOL) of this decision. We will measure 1) Cancer-specific HRQOL using the *validated*, and well-published instrument Prostate Cancer Symptom Indices (PCSI).²⁷⁻³⁴ PCSI measures treatment-related morbidity,³⁴ and is comprised of scales which measure sexual, bowel and urinary symptoms. In each scale, patient answers are converted to a score from 0 (no symptom) to 100 (maximum symptoms). 2) Global HRQOL will be measured by the *validated* Short-Form 12 (SF-12), one of the most frequently used HRQOL instruments in medicine, and has been used frequently in prostate cancer.³⁵ SF-12 provides the Mental (MCS) and Physical Component Summary scores (PCS), calculated using norm-based scoring, with the mean score 50 and standard deviation 10.^{36,37} A lower score indicates lower HRQOL.

NC ProCESS contains complete PCSI and SF12 data at baseline (pre-treatment), and 12 months after treatment; and MAX-PC data at 12 months. NC ProCESS continues to collect these data at 12-month interval time points. By the end of this proposed study, all participants will complete 60-month (5-year) data collection; these data will be available for Aim 2 analysis.

Covariates [IR-3][CI-4]: Data collected at the time of diagnosis by the NC ProCESS include

From Cancer Registry: county of residence;

[figure not shown]

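### Aim 2 adjusts the MAX-PC analysis for pre-treatment anxiety only if the surveillance groups are seen to differ on it, although the plan itself names baseline anxiety as a likely confounder

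*Combined protocol and SAP*

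**What the plan says.** In Specific Aim 2, Potential problems and alternative strategies, the plan states: "Patients with different baseline HRQOL and anxiety may receive different surveillance frequencies". It notes that MAX-PC, the Aim 2 primary outcome, was not collected before treatment. As a substitute it "will examine if pre-treatment anxiety (an item on SF-12) differs by surveillance frequency groups", and continues: "If so, we will adjust for this baseline anxiety measure in data analysis". It does not say what test, threshold or size of difference would trigger adjustment.

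Under Aim 2 Data Analysis, the repeated-measures models have a fixed covariate set: "Models will account for the covariates described above". The written list under Aim 2 Covariates covers county of residence, medical-record items (age, comorbidity, risk group, treatment) and this line: "From patient report: education, household income, race/ethnicity, insurance, marital status, employment". It has no baseline anxiety or SF-12 measure. The item is available, since Aim 2 Outcomes says "NC ProCESS contains complete PCSI and SF12 data at baseline (pre-treatment" and at 12 months.

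For Aim 1, the corresponding Data Analysis sentence reads: "We will examine if surveillance frequency is associated with each individual factor and account for these factors using modeling as above". Aim 1 also intends to place prognostic features in the primary analysis, as model covariates or in the propensity score. Section C3 plans propensity-score weighting and matching for all outcomes, as sensitivity analyses. The footnote to Figure 3 says of Aim 2: "Analyses will be stratified by the type of initial treatment (surgery, radiation) and recurrence risk (low, intermediate, high" risk).

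**The concern.** The rule is a preliminary test for confounding. A covariate the plan expects to influence exposure is left out of the primary model unless the data show a group difference. Failure to detect a difference does not show that there is none, and the check is weakest where groups are small.

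The item matters because nothing else in the primary model stands in for it. Surveillance groups are defined by PSA tests in the first year after treatment, and MAX-PC is first measured at 12 months, around the end of that window. The first MAX-PC score is therefore not a pre-exposure baseline. If more anxious men are tested more often, omitting the item biases the result towards the Aim 2 hypothesis that frequent surveillance raises anxiety.

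There is also a precision cost. A baseline measure correlated with the outcome reduces residual variance whether or not the groups differ on it, and the rule gives this up whenever the check is negative.

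**Working it through.** **The plan's own figures.** 1,079 × 0.75 = 809.25, the stated N = 809. The smallest low-risk share in Table 2 is 19%: 809 × 0.19 = 153.7, the stated 154. With 154 per group and a 0.5 SD difference, power = Φ(0.5 × √(154/2) − 1.960) = Φ(2.43) = 99.2%. The stated 90% is therefore a floor. None of this changes with the adjustment rule.

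**Inputs.** From the documents: N = 1,079 at 12 months; N = 809 completers; Table 2 shares (1 / 2-3 / 4 tests: 20/61/19% low, 18/59/23% intermediate, 17/53/30% high risk); six strata (2 treatments × 3 risk groups); 0.5 SD target. Assumed: the check is a two-sided 5% two-group test; true baseline gap δ = 0.2-0.3 SD; correlation r = 0.3-0.5 between the item and MAX-PC; an average stratum of 1,079/6 ≈ 180 men.

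**How often the check misses a real gap.** With s = √(1/n₁ + 1/n₂) and λ = δ/s, P(miss) = Φ(1.96 − λ) − Φ(−1.96 − λ). Example, low-risk shares, N = 1,079, 1 versus 4 tests (216 v 205): s = 0.0975, λ = 0.2/0.0975 = 2.05, P(miss) = Φ(−0.09) − Φ(−4.01) = 0.46.

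**Mean bias under the rule, item measured without error.** Bias arises only when the check is negative, so bias = r × E[observed gap × 1(|z| < 1.96)], where the expectation = δ·P(miss) + s·[φ(−1.96 − λ) − φ(1.96 − λ)]. Same example: 0.2 × 0.464 − 0.0975 × 0.397 = 0.054; times 0.3-0.5 gives 0.016-0.027 SD.

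All three pairs under all three Table 2 columns:

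| Setting | δ (SD) | P(miss) | Expectation (SD) | Bias, r = 0.3-0.5 (SD) |
|---|---|---|---|---|
| N = 1,079 | 0.2 | 0.18-0.46 | 0.018-0.054 | 0.005-0.027 |
| N = 1,079 | 0.3 | 0.01-0.13 | 0.001-0.019 | below 0.01 |
| N = 809 | 0.2 | 0.30-0.57 | 0.032-0.070 | 0.010-0.035 |
| Stratum, about 180 | 0.2 | 0.78-0.87 | 0.107-0.125 | 0.03-0.06 |
| Stratum, about 180 | 0.3 | 0.58-0.76 | 0.107-0.154 | 0.03-0.08 |

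The unadjusted stratum standard error, s, is 0.17-0.24 SD, so the stratum bias is about a third of one standard error or less. A single three-group test (means 0, 0.1, 0.2 SD) misses 51-57% pooled and 88-89% per stratum.

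**Simulation of the plan's rule against always adjusting** (true effect zero; 10,000 runs pooled, 20,000 per stratum; two-group comparison of means, no other covariates):

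- Item error-free: always adjusting is essentially unbiased. Rejection under the plan's rule is 4.2-6.2%. Always adjusting cuts the standard error by 2.7-10.4% with no gap, 2.0-8.5% at 0.2 SD and 0.4-7.6% at 0.3 SD.
- Item reliability 0.6 (assumed), pooled, 0.2 SD gap: bias is 0.034-0.065 SD under the rule and 0.023-0.041 SD when always adjusting, a gain of 0.011-0.025 SD. Rejection is 6.7-11.7% against 5.6-8.8%. Across settings at this reliability the standard-error saving is 0.7-6.0%.

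**The case against.** The best counter-argument is that the effect is too small to matter. Pooled bias is a few hundredths of an SD against a 0.5 SD target, false positives stay near 5% if the item is error-free, and larger gaps are more often detected (at 0.3 SD with N = 1,079, only 1-13% are missed). If the item is measured with error, most of the remaining bias comes from that error and survives the fix. Pooled power at 0.5 SD already exceeds 99%, so the precision gain changes no conclusion at the target. These points stand, and they limit the importance of the concern.

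Other points stand in part:

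- The models also address change from the first time point to 60 months. A baseline trait that shifts every MAX-PC score equally cancels from a group-by-time contrast. But the plan also compares overall scores between groups, and that comparison is exposed.
- The plan says pre-treatment data make it possible to account for baseline differences. This states a capability; the only rule given for anxiety is the conditional one.
- The propensity analyses select confounders and outcome predictors, C3 adds variables that remain unbalanced, and an unmeasured-confounder analysis is listed for Aim 2. These mitigate, but they are sensitivity analyses and do not name the item.
- The contrast with Aim 1 is not perfect: Aim 1 also examines associations first, and qualifies its control variables as used where appropriate. Still, it does not make adjustment conditional on the finding.
- The 5% test is an assumption. C3 names t-tests and chi-squared or Fisher's tests for balance, and standardised differences for the matched sample, but the Aim 2 text names no method.
- Figure 3, and a figure beside the covariate list, were not visible in the copy reviewed. Either may show baseline anxiety, but neither would cancel the written condition.

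**Conclusion.** The concern holds. The plan names baseline anxiety as a possible cause of surveillance frequency, then makes its inclusion in the primary-outcome analysis depend on an undefined check that can easily miss a relevant imbalance, above all if Aim 2 is analysed by stratum.

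The consequence is modest. With an error-free item, a 0.2 SD gap leaves a mean bias of at most about 0.03 SD at N = 1,079 (some 5% of the target) and 0.035 SD at N = 809 (7%). In strata, bias reaches 0.03-0.08 SD for gaps of 0.2-0.3 SD. Always adjusting would also lower the standard error by up to about 10%, and by less if existing covariates already explain part of the outcome. These figures rest on the assumed test, gaps, correlations and reliability, and apply to comparisons of score levels. This is an avoidable weakness in specification that should be corrected; it does not show a large error in the result.

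**What to change.** List the pre-treatment SF-12 anxiety item among the Aim 2 covariates and include it in the primary MAX-PC model in every case, with no preliminary test. Where it is missing, use the multiple imputation already planned in C3. Keep the comparison of the item across surveillance groups, labelled as descriptive. State that adjustment by a single item is partial, so some confounding by baseline anxiety may remain.

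The cost is SAP wording only, because the item is already collected. The model gains one covariate, a small burden in strata where the smaller groups have about 30 men (for example 180 × 0.17 ≈ 31).
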